10.3 Other study parameters

Demographic data, pre-operative NRS scores, perioperative administered cumulative drugs dosage and length of admission (at PACU, ICU and/or ward) will be reported.

Continuous normally distributed variables will be expressed by their mean and standard deviation or when not normally distributed as medians and their interquartile ranges. Categorical variables will be expressed as n (%). To test groups Student's t test will be used, if continuous data are not normally distributed the Mann-Whitney U test will be used. Categorical variables will be compared with the Chi-square test or Fisher's exact tests. P-values < 0.05 will be considered significant.

Data analysis will be performed using R Studio, Boston, MA, USA..

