8.1.1 Secondary study parameters/endpoints

To study the effect of deep neuromuscular block as compared to standard neuromuscular block on:

- Surgical working conditions (L-SRS, Table 3)
- 30-day post-operative complications (Clavien-Dindo, Table 6)
- 30-day post-operative complications according to the Comprehensive Complication Index
- 30-day unplanned readmission rates
- Quality of recovery at post-operative day 1, 2 and 30 after laparoscopic surgery.
 - Quality-of-recovery (QoR-40 at postoperative day 1 and 2; Aldrete score (Table 5) at the PACU)
 - Quality-of-life at postoperative day 30 (SF36, Appendix 2)

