8.1.2 Other study parameters

- Patient age, gender, length and weight, ASA class, underlying disease(s), planned procedure, blood pressure and heart rate, center of admission
- Pre-operative NRS, QoR-40 and SF 36
- Per operative the following variables will be noted, after installation of the pneumoperitoneum at 15 minute intervals until the end of the surgery. At these moments the L-SRS is also scored:
 - Heart rate (/min), blood pressure in mmHg
 - Intra-abdominal pressure in mmHg and total insufflations volume (in Liters)
 - Depth of anesthesia: Bispectral Index and end-tidal sevoflurane
 - Depth of NMB (TOF count and/or PTC)
 - Duration of surgery and anesthesia
 - Time of extubation
 - Cumulative drug dosages (propofol, opioids, muscle relaxant, reversal agent, inotropics, NSAIDS's or metamizol)
 - Core temperature in degrees Celsius
 - Surgical satisfaction with the anesthesia: 'very dissatisfied', 'dissatisfied', 'satisfied' tot 'very satisfied'.
- Postoperative recovery scores:
 - Time to discharge readiness (Aldrete score ≥ 9 and NRS < 5)
 - Heart rate (/min), blood pressure in mmHg
 - peripheral oxygen saturation, respiratory rate (/min), use of supplemental O₂ (in liters/minute)
 - NRS and administration of analgesic medication
 - Ramsay sedation scale and Aldrete score
 - Nausea or vomiting

- Length of admission at the PACU and/or ICU (if applicable) and duration of hospital admission
 - Pain scores (numeric rating scale; NRS 0 no pain – 10 worst pain imaginable) at movement (and rest) three times daily until discharge or to a maximum of 72 hours will be extracted from the patient clinical charts.
 - Medication use (three times daily until discharge or to a maximum of 72 hours) will be extracted from the patient clinical charts.
 - Cumulative opiate use
 - Cumulative use of other analgesics and anti-emetics

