10.2 Secondary study parameters

Continuous normally distributed variables will be expressed by their mean and standard deviation or when not normally distributed as medians and their interquartile ranges. Categorical variables will be expressed as n (%). To test groups Student's t test will be used, if continuous data are not normally distributed the Mann-Whitney U test will be used. Categorical variables will be compared with the Chi-square test or Fisher's exact tests. P-values < 0.05 will be considered significant for the primary outcome. A cut off p-value of < 0.01 will be applied for secondary outcomes.

Data analysis will be performed using R Studio, Boston, MA, USA..

Longitudinal data (heart rate, blood pressure, L-SRS, BIS levels compared to the depth of NMB at the given moment) will be analyzed using linear mixed models. NONMEM (ICON Development Solutions, Ellicott, MD, USA), will be used for statistical analysis.

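### Section 10.3 calls 'other' parameters significant at p < 0.05 while the higher-ranked secondary outcomes need p < 0.01, and the Aldrete score is listed in both tiers

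*Combined protocol and SAP*

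**What the plan says.** The combined protocol and SAP sets a cut-off for each of three tiers.

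- **Primary.** Section 10.1 uses a chi-square test at the 5% level, and 10.2 repeats the rule: "P-values < 0.05 will be considered significant for the primary outcome".
- **Secondary.** Section 10.2 adds: "A cut off p-value of < 0.01 will be applied for secondary outcomes".
- **Other.** Section 10.3 opens with "Demographic data, pre-operative NRS scores, perioperative administered cumulative drugs dosage and length of admission (at PACU, ICU and/or ward) will be reported". It then repeats the tests of 10.2 (t, Mann-Whitney, chi-square, Fisher) and states "P-values < 0.05 will be considered significant".

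No reason is given for the different cut-offs, and nothing in 10.3 marks its results as exploratory.

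The Aldrete score appears in two endpoint lists. Section 8.1.1 places it among the secondary endpoints, under quality of recovery: "Aldrete score (Table 5) at the PACU". Section 8.1.2, headed *Other study parameters*, lists it again among the postoperative recovery scores: "Ramsay sedation scale and Aldrete score". It also uses the score to define time to discharge readiness. The secondary objectives in section 2 do not mention it.

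**The concern.** A graded set of cut-offs normally asks for at least as much evidence lower down the hierarchy as higher up. Here the order reverses at the last step. The secondary endpoints, which have hypotheses stated in section 2, need p < 0.01. The list below them, which has none, needs only p < 0.05.

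What is at stake is how results are labelled. A shorter stay or a lower opioid dose at p = 0.03 would be reported as significant, while a better QoR-40 at the same p-value would not. Several of the other parameters lie close in meaning to recovery, so they could be presented alongside the quality-of-recovery hypothesis on a weaker standard of proof. A variable in both lists adds a second problem: its label could be chosen after the p-value is known.

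**Working it through.** The plan computes no figure on this point. The cut-offs are stated rules, so the first step is to set them side by side.

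**1. Cut-offs by tier**

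| Tier | Section | Cut-off | Two-sided critical z |
|---|---|---|---|
| Primary | 10.1, 10.2 | 0.05 | 1.96 |
| Secondary | 10.2 | 0.01 | 2.58 |
| Other | 10.3 | 0.05 | 1.96 |

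The bottom tier's cut-off is 0.05 / 0.01 = 5 times looser than the tier above. For a continuous variable at the planned 439 per arm, the smallest difference that reaches significance is z × √(2/439) = z × 0.0675 standard deviations. That is 1.96 × 0.0675 = 0.13 SD in the other tier and 2.58 × 0.0675 = 0.17 SD in the secondary tier.

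**2. How many variables fall under 10.3?** The text allows two readings.

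- *Narrow: only what 10.3 names.* Section 8.1.2 lists six drug groups (propofol, opioids, muscle relaxant, reversal agent, inotropics, NSAIDs or metamizol), and 10.3 gives three lengths of admission (PACU, ICU, ward): 6 + 3 = 9. Muscle relaxant and reversal dose differ between arms by design (section 5), so they cannot be true nulls: 9 − 2 = 7.
- *Broad: the whole of 8.1.2 through the shared heading.* My count of post-randomisation variables is 18 intra-operative, 11 at the PACU, 3 lengths of stay and 5 on the ward: 18 + 11 + 3 + 5 = 37. Three differ by design (depth of block, relaxant dose, reversal dose), and three are modelled under 10.2 (intra-operative heart rate, blood pressure, BIS). Removing them leaves 37 − 6 = 31, or 30 without the Aldrete score. The count depends on how items are split, so I use 30 to 40.

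**3. False positives if all k nulls are true.** The expected number is k × α, which needs no independence. The chance of at least one is 1 − (1 − α)^k, which assumes independence.

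| k | Expected, 0.05 | Expected, 0.01 | At least one, 0.05 | At least one, 0.01 |
|---|---|---|---|---|
| 7 | 0.35 | 0.07 | 1 − 0.95^7 = 30.2% | 1 − 0.99^7 = 6.8% |
| 30 | 1.5 | 0.3 | 1 − 0.95^30 = 78.5% | 1 − 0.99^30 = 26.0% |
| 40 | 2.0 | 0.4 | 1 − 0.95^40 = 87.1% | 1 − 0.99^40 = 33.1% |

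Pain scores, analgesic use and discharge readiness are plainly related, so the last two columns are illustrative.

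**4. The Aldrete score.** Section 8.1.1 with 10.2 gives 0.01. Section 8.1.2 with 10.3 gives 0.05, but only if the shared heading carries the 10.3 rule to everything in 8.1.2, because 10.3 does not name the score. On that reading, any result with 0.01 ≤ p < 0.05 has two possible labels. Heart rate, blood pressure and BIS raise a similar question: 8.1.2 lists them as other parameters, while their mixed-model analysis sits in 10.2.

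**The case against.** The strongest reply has four parts.

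- **The Aldrete score has one explicit home.** Section 8.1.1 names it a secondary endpoint. Section 8.1.2 reads largely as a data-collection list and also mentions the L-SRS, QoR-40 and SF-36, which belong to secondary endpoints, so a mention there need not assign a tier. This largely stands. A reader might infer that a p-value of 0.03 is both significant and not significant under the plan. The documents do not go that far: the conflict runs only through a shared heading. What remains is an ambiguity that no sentence resolves.
- **A count of 30 to 40 tests is the widest reading.** This stands, and the narrow figure belongs beside it. The reversal does not depend on the count, because drug doses and lengths of admission are named in 10.3 itself. If the narrow reading is right, the rest of 8.1.2 has no stated cut-off at all.
- **Secondary endpoints keep their own rule.** This stands in full. A reader might infer that the looser tier undoes multiplicity protection for the secondary outcomes. It does not: they still need p < 0.01, and their error rate does not change. Nor does the plan say that 0.01 was chosen as a multiplicity correction.
- **Exploratory results need no correction.** That is an argument for dropping the significance label, not for a formal declaration at 0.05.

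A reader might also infer that the plan tests demographic data between arms. Section 10.3 says these data are reported, and its testing sentences are generic wording repeated from 10.2. Baseline testing is a possible reading, not a stated intention.

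**Conclusion.** The reversal of cut-offs is stated outright in 10.2 and 10.3, and the concern holds at that level. As written, at least the cumulative drug doses and lengths of admission would be called significant on weaker evidence than the hypothesised secondary endpoints. PACU pain and discharge readiness join them only if 10.3 governs all of 8.1.2.

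The size depends on that reading: roughly a fourfold difference in the chance of a false positive if 10.3 is narrow, and roughly a threefold difference at a much higher level if it is broad. Both rest on true nulls and independence; only the expected counts are free of the second assumption. The Aldrete score's threshold is ambiguous rather than flatly contradictory.

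The effect is confined to the labelling of lowest-tier results and of the Aldrete score. The primary test, its alpha and the sample size are untouched. The wording should be corrected before analysis, but the point does not threaten the trial's main conclusion.

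**What to change.** Change the SAP wording as follows.

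1. In 10.3, replace the p < 0.05 rule with between-arm estimates and 95% confidence intervals, labelled exploratory, with no claim of significance. If a cut-off is kept, make it no looser than 0.01. Say whether 10.3 covers the whole of 8.1.2.
2. State that the Aldrete score is analysed once, as a secondary endpoint at 0.01. In the same sentence, give the tier of heart rate, blood pressure and BIS.
3. State that demographic and pre-operative variables are summarised by arm without tests.

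Conduct, data collection and sample size do not change. The price is fewer nominally significant exploratory results. If the 0.01 option is taken, for example, power for an assumed difference of 0.2 SD at 439 per arm falls from Φ(0.2/0.0675 − 1.96) = 84% to Φ(0.2/0.0675 − 2.58) = 65%. That option also still leaves the 26-33% chance of at least one false positive on the broad reading, which is a reason to prefer estimates without a label.

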10.4 Interim analysis

No planned interim analysis will be performed.

11. ETHICAL CONSIDERATIONS

11.1 Regulation statement

This study will be conducted according to the principles of the Declaration of Helsinki as stated in the current version of Fortaleza, Brazil, 2013 and in accordance with the Medical Research Involving Human Subjects Act (WMO).

11.2 Recruitment and consent

Only adults who are not incapacitated are recruited after initial screening at the preoperative screening visit. All possible study candidates will receive a copy of the patient information sheet and a copy of the consent form, at a considerable time before surgery. Patient consent will be obtained, in person, before surgery by one of the researchers.

11.3 Benefits and risks assessment, group relatedness

Not applicable

11.4 Compensation for injury

In this study two common practices are compared that are deemed safe. Hence there are no potential issues of concern and insurance according to Article 7 WMO is not required in this study.

11.5 Incentives

Not applicable

12.2 Monitoring and Quality Assurance

On-site monitoring will comprise controlling presence and completeness of the research dossier and the informed consent forms, source data checks will be performed as described in the monitoring plan. Every participating centre will be visited at least once every year. The monitor of this study in the LUMC is selected out of the monitoring pool of the LUMC. The other study sites will be monitored by a trained monitor not involved in the study. The details of monitoring will be described in the monitoring plan.

12.3 Amendments

A 'substantial amendment' is defined as an amendment to the terms of the METC application, or to the protocol or any other supporting documentation, that is likely to affect to a significant degree:

- the safety or physical or mental integrity of the subjects of the trial;
- the scientific value of the trial;
- the conduct or management of the trial; or
- the quality or safety of any intervention used in the trial.

All substantial amendments will be notified to the METC and to the competent authority.

Non-substantial amendments will not be notified to the accredited METC and the competent authority, but will be recorded and filed by the sponsor.

12.4 Annual progress report

The sponsor/investigator will submit a summary of the progress of the trial to the accredited METC once a year. Information will be provided on the date of inclusion of the first subject, numbers of subjects included and numbers of subjects that have completed the trial, serious adverse events/ serious adverse reactions, other problems, and amendments.

12.5 Temporary halt and (prematurely) end of study report

The investigator/sponsor will notify the accredited METC of the end of the study within a period of 8 weeks. The end of the study is defined as the last patient's last visit.

The sponsor will notify the METC immediately of a temporary halt of the study, including the reason of such an action.

In case the study is ended prematurely, the sponsor will notify the accredited METC within 15 days, including the reasons for the premature termination.

Within one year after the end of the study, the investigator/sponsor will submit a final study report with the results of the study, including any publications/abstracts of the study, to the accredited METC.

12.6 Public disclosure and publication policy

The study protocol and analysis plan will be published before start of the study on clinicaltrial.gov (trialnumber: tbd). The results of the study will find their way into (inter-) national scientific journals

and guidelines. We will submit analyses to scientific journals in the field of anaesthesiology. The results of this study will be disclosed unreservedly according to the Central Committee on Research Involving Human Subjects (CCMO) statement on publication policy (<http://www.ccmo.nl/attachments/files/ccmo-statement-publicatiebeleid-3-02-en.pdf>).

Material for public dissemination will be submitted to the sponsor for review prior to submission for publication.

13. STRUCTURED RISK ANALYSIS

13.1 Potential issues of concern

In this study two common practices are compared that are deemed safe. Hence there are no potential issues of concern.

